8.4 Final Study Visit (Week 96 +/- 14 days)

The duration of the study is 2 years per participant. Participants will be recruited during the first year of the study and will be followed for 96 weeks. The final visit will be the participant's last follow-up visit and the following assessments will take place:

- Complete Physical Exam
- Vital Signs
- Hematology and biochemistry: CBC with differential and liver profile (AST, ALT), serum creatinine, calcium, phosphate, Urinalysis, GFR, Urine albumin/creatinine, urine protein/creatinine, lipids- cholesterol, LDL, HDL, TG, glucose. CD4/CD8
- Urine pregnancy test and FSH (if premenopausal)
- HIV Viral Load
- Research Blood Sample
- Questionnaires- quality of life, adherence, falls, balance
- Frax Score determined by country specific FRAX calculator
- Framingham Cardiovascular Risk Score
- Medication review: ART and Other Concomitant Medications
- Imaging as per study site: DXA, TBS, HRpQCT
- Geriatric assessment, with questionnaires (frailty, quality of life, balance, falls), dynamometer, performance walking test.

To collect any information on potential adverse event reaction, patients will be called 4 weeks after their last visit at 96 weeks +/- 7 days.

8.5 Early Termination

If a participant withdraws from the study early, documentation for reason of early termination is required. Investigations will be completed as per final visit.

8.6 Re-contact of Participants after Study Termination

Study results will be made known to the site investigators. As per site practices and IRB/REB requirements, site investigators will be responsible for disseminating the information to participants who participated in the study.

8.7 Schedule of Procedures

Study Weeks		W0	W4	W12	W24	W36	W48	W52	W60	W72	W84	W96/End of Study	W100
Study Visits	Screening (-30 days)	Baseline (screening + 30 days)											
Visit Duration	1-2 hours	2 hours	1 hour	1 hour	1 hour	1 hour	1-2 hours	1 hour	1 hour	1 hour	1 hour	1-2 hours	Phone call
Informed Consent Form	X												
Assign Subject ID number	X												
Randomization		X											
Demographics	X												
FRAX and Framingham Score	X						X					X	
Medical History	X												
Physical Exam ¹ Signs/ Symptoms	X (complete)	X	X	X	X	X	X (complete)	X	X	X	X	X (complete)	
Vital Signs including height, weight and determination of BMI	X	X	X	X	X	X	X	X	X	X	X	X	
Pregnancy test (if premenopausal), FSH	X ²	X	X	X	X	X	X ²	X	X	X	X	X ²	
HIV viral load ³	X	X ³	X ³	X	X	X	X ³	X ³	X	X	X	X ³	
CD4/CD8 count ³		X ³		X	X	X	X ³	X	X	X	X	X ³	
Hematology and biochemistry: CBC with differential and liver profile (AST, ALT, serum creatinine, calcium, phosphate, Urinalysis, GFR, Urine albumin/creatinine) ³	*X	X ³	X	X	X	X	X ³	X	X	X	X	X ³	
HBsAg, anti-HBcAb, HBsAb, HCV antibody ⁴	X ⁴												

Study Weeks		W0	W4	W12	W24	W36	W48	W52	W60	W72	W84	W96/End of Study	W100
Fasting glucose/cholesterol ³		X ³					X ³					X ³	
Research blood sample		X					X					X	
Study Drug dispensation		X		X	X	X	X	X	X	X	X	X	
Study Drug Accountability (pill counts)			X	X	X	X	X		X	X	X	X	
Questionnaires/assessments (calcium & vitamin D ⁵ , quality of life, adherence, frailty, falls, balance)	X ⁵	X					X					X	
Concomitant Medication review	X	X	X	X	X	X	X	X	X	X	X	X	
Dexa scan ⁶	X ⁶						X					X	
Trabecular bone score determined from DXA (participating sites)		X					X					X	
HRQCT scan (participating sites)		X					X					X	
Grip strength with dynamometer		X					X					X	
Test of balance and gait- balance tests, gait speed, chair stand		X					X					X	
Capture adverse events or changes in clinical conditions/medications		X	X	X	X	X	X	X	X	X	X	X	X

¹Targeted physical exam except at Screening, Weeks 48 and 96/end of study

² Serum pregnancy and FSH for all participants at screening. Urine pregnancy at all other visits, and FSH at Weeks 48 and 96/end of study **for pre-menopausal women only**

³Screening lab results may be within 1 month of screening visit. Lab collection and results as per site Standard of Care, except at Weeks 0, 48 and 96 (end of study) where lab collection and results are required. Repeat viral load and safety assessments should be done at Weeks 4 and 52.

⁴ HBV and HCV status to be tested at screening **only if NOT** previously done

⁵ Calcium & Vitamin D assessment should be done at Screening. All other questionnaires at Weeks 0, 48 & 96/end of study

⁶ Baseline Dexa Scan should be completed prior to baseline visit

9.0. STUDY DRUG

Participants will take a single tablet of FTC/TDF (300/200mg) or FTC/TAF (200/**10** mg) if the third agent is a ritonavir boosted protease inhibitor, or 200mg/**25** mg if the third antiretroviral agent is an NNRTI, raltegravir or dolutegravir) ²⁴ once daily orally with the recommended dose of the co-administered third agent. For those previously on EVG/c/TDF/FTC or RPV/TDF/FTC, you will continue to receive EVG/c/TDF/FTC or RPV/TDF/FTC, or switch to EVG/c/F/TAF or RPV/F/TAF.

After 48 weeks all participants will take a single tablet of FTC/TAF (200mg/10 mg if the third agent is a ritonavir boosted protease inhibitor or 200mg/25 mg if the third agent is an NNRTI, raltegravir or dolutegravir), EVG/c/F/TAF, or RPV/F/TAF once daily.

Study drug will be donated by Gilead. Study drug will be packaged in bottles containing 30 tablets, silica gel desiccant and polyester packing material. Each bottle will be enclosed with a polypropylene screw cap. To ensure stability the drug should not be stored in any other container than that supplied. The study drug bottles will be labelled to meet all the applicable requirements of the EU guidelines to good manufacturing practice, Health Canada and the US food and drug administration. The bottles should be stored at a controlled room temperature of 25C (77F) with excursions permitted to between 15C and 30C). Storage conditions will be specified on the labels.

Until dispensed to participants, all bottles of study drug will be stored in a securely locked area, accessible only to authorized study personnel.

The third ARV agent of the participants pre-existing regimen should be taken and stored according to the approved product labeling for each particular component.

9.1 Study Drug Accountability

The investigator at each site is responsible to ensure adequate accountability of all used and unused study products. The investigator or designated central pharmacy will acknowledge receipt of the study drugs from Gilead after reviewing the shipment's content and condition. Study sites will acknowledge receipt of study drugs from the UHN Central Pharmacy after reviewing the contents and condition of the shipment. The investigator or designee will be responsible for maintaining an accurate inventory of the dates and quantities of all study drugs received, dispensed and returned. Each dose of the study drug administered by the qualified study centre personnel will be accurately recorded on logs which indicate the date and quantity of all doses dispensed. These logs will be available for inspection by study monitors. Study medication supplies must be accounted for by the study monitor prior to destruction or return.

10. EARLY TERMINATION

Participation in the study will be terminated early if: the participant refuses further treatment and/or follow-up evaluations; the study staff or participant's medical provider determines that further participation in the study would be detrimental to the participant's health or well-being; the participant is non-compliant with the study requirements in a manner that is either detrimental to her health or interferes with the validity of the study results; the patient has viral failure and requires an alternative antiretroviral regimen (the viral load that requires a change in therapy will be at discretion of the investigator), or the sponsor terminates the study.

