8.3 Follow-up Visits for Participants

These will occur at weeks 4, 12, 24, 36, 48, 52, 60, 72, 84 and 96. At weeks 4, 12, 24, 36, 52, 60, 72, and 84, the participants will have routine investigations as per the study site, and will complete targeted physical exams. **Complete** physical exams, labwork as outlined in the schedule of Assessments on pages 25 – 26, and FSH (if premenopausal) will be required at weeks 48 and 96. Adverse events will be captured at each study visit as will any changes in clinical conditions or medications. Pill counts of returned study drug except week 52 will also be captured. The accepted windows around study visits are +/- 7 days. The procedures will last about 60 minutes.

If they agree, participants will continue to be followed even if they decide to stop the study medication

At weeks 48 and 96 all participants will complete the study imaging, collection of plasma specimens for marker banking, quality of life questionnaires, FRAX score as determined by country specific FRAX calculator, Framingham cardiovascular risk score, and geriatric measures as above. The additional procedures will last

approximately 30 minutes plus imaging time. The imaging is to be scheduled within 4 weeks of these visit dates.

Drug dispensation will be done every 3 months during the regular visits at W0, 12, W24, W36, W48, W60, W72, and 84. At week 48, all participants will receive open label TAF/FTC.

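### Section 10 ends study participation when a woman refuses treatment alone, contradicting 8.3, and has no follow-up clause for its non-compliance and viral-failure triggers, so obtainable week-48 DXAs can be lost

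*Combined protocol and SAP*

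**What the plan says.** Section 10 is the protocol's termination rule. It governs participation in the study, not only study drug, and is worded as mandatory. Three of its triggers matter here:

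- Refusal: "Participation in the study will be terminated early if: the participant refuses further treatment and/or follow-up evaluations".
- Non-compliance, with a qualifier: "the participant is non-compliant with the study requirements in a manner that is either detrimental to her health or interferes with the validity" of the results.
- Viral failure, with a qualifier: "the patient has viral failure and requires an alternative antiretroviral regimen", the viral load that calls for a change being left to the investigator.

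Section 8.3 says that, if they agree, "participants will continue to be followed even if they decide to stop the study medication". Section 11.6 covers TAF/FTC stopped for suspected renal impairment or other chemistry elevations. It withdraws such women from the study and then, in the next sentence, keeps them in follow-up to the end if they agree. Section 11.7 leaves management of viral failure to the investigator and allows the regimen to continue with adherence support in some cases.

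For a woman who withdraws early, section 8.5 says: "Investigations will be completed as per final visit". The final-visit list in 8.4 includes DXA, and 8.4 adds: "The final visit will be the participant's last follow-up visit".

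The primary endpoint (5.4) is the percent change in lumbar spine BMD from baseline to week 48. Section 13.7 expects 10% dropout before week 48, assumes missing at random for the primary analysis, and plans pattern mixture and selection models as sensitivity analyses.

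**The concern.** Take a woman who stops study drug at week 20 and is willing to come for her week-48 scan. Section 8.3 keeps her; section 10 ends her participation. The protocol does not say which section prevails, so sites may handle the same woman differently.

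The week-48 DXA is at stake. The schedule in 8.7 places DXA at screening, week 48 and week 96 only, and each woman gives the 13.2 model her week-48 and week-96 changes. A woman whose participation ends before week 48 therefore has no scheduled post-baseline value. Her reason for leaving (refusal, non-compliance or viral failure) arose after randomisation and is plausibly related to outcome. The covariates in 13.2 are arm, week, their interaction and country, with hormone therapy optional, so for these women missing at random rests on little else. The sensitivity models in 13.7 can vary that assumption, but they cannot supply scans that 8.3 would have collected.

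**Working it through.** **Comparing the rules**

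| Trigger in section 10 | What other sections say | Result |
|---|---|---|
| Refuses treatment, would attend visits | 8.3: follow-up continues if she agrees | Direct contradiction |
| Non-compliance that harms her or threatens validity | 8.3 speaks only of deciding to stop drug | No word-for-word conflict; no follow-up clause |
| Viral failure requiring a new regimen | 11.7 allows treatment to continue in some cases and is silent on follow-up after a change | No word-for-word conflict; no follow-up clause |

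**Reproducing the plan's figure**

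Inputs from 13.1: difference d = 1 point, SD = 2, alpha = 0.05 (taken as two-sided), two-sample t test, 64 per arm. Power comes from the noncentral t distribution with 2n − 2 degrees of freedom and noncentrality d / (SD × √(2/n)).

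- n = 64: 1 / (2 × √(2/64)) = 2.83, power 80.1%.
- n = 63: power 79.5%.

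So 64 per arm is the right answer for 80% power with complete data.

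**Illustrating the stake**

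The protocol's 10% dropout is all-cause: 0.10 × 128 = 12.8 women. The share due to section 10 is not given. Let f be the share of each arm that stops drug or changes regimen, and k the share of the effect that these women keep. Both are assumptions.

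- If they are lost and the retained women show the full effect: n = 64(1 − f), d = 1.
- If they are followed and analysed as randomised: n = 64, d = 1 − f(1 − k).

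| f | Women per arm (64f) | Lost: n per arm, power | Followed, k = 0: d, power | Followed, k = 0.5: d, power |
|---|---|---|---|---|
| 2% | 1.3 | 62.7, 79.3% | 0.98, 78.5% | 0.99, 79.4% |
| 5% | 3.2 | 60.8, 78.1% | 0.95, 76.0% | 0.975, 78.1% |
| 10% | 6.4 | 57.6, 75.8% | 0.90, 71.4% | 0.95, 76.0% |

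With k = 1 the followed case returns to 80.1%. The retained-only estimate exceeds the as-randomised difference by f(1 − k): from 0.02 × 0.5 = 0.01 to 0.10 × 1 = 0.10 points, and by nothing if k = 1. The SD is held at 2; allowing for the mixture of women on and off effect lowers the 71.4% to 71.0%. The sums also assume that stopping drug does not change BMD in the delayed arm.

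**The exit scan**

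The visit window is "The accepted windows around study visits are +/- 7 days", and for imaging, "The imaging is to be scheduled within 4 weeks of these visit dates". On those terms a week-48 scan would be scheduled no earlier than about week 48 − 1 − 4 = 43. An exit DXA is taken at withdrawal, which may be well before that. Section 13.2 does not say whether or how such a scan enters the model.

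**The case against.** The strongest reply is that the protocol already shows what it wants. Section 8.3 is the specific rule for women who stop drug. Section 11.6 uses withdrawal from the study in a sense that does not end follow-up, so section 10 can be read the same way. That reading is reasonable and some sites will adopt it. It does not settle the matter: section 10 is the dedicated termination rule, is mandatory in form and carries no cross-reference to 8.3 or 11.6. This is why the point is that scans can be lost, not that they will be.

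A second reply is that early withdrawals do get a DXA under 8.5. They do, and that limits the loss. But a scan at withdrawal is a poor stand-in for week 48, and no rule makes it one. A reader might go further and infer from the imaging window that a scan before about week 43 cannot count. The documents do not support that: the four weeks are a scheduling instruction, and 13.2 sets no analysis window.

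A third reply is that the gap of up to 0.10 points is a difference between two target quantities (retained women and all randomised women), not a demonstrated bias, and that it rests on assumed shares. This stands. The top case needs the whole 10% dropout to be women who leave under section 10, could have been scanned and keep none of the effect. Nor is 0.10 a bound: section 1.1 links continued TDF use to further BMD loss, so a delayed-arm woman who stops TDF may well change.

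**Conclusion.** The point holds. For refusal of treatment, section 10 contradicts 8.3. For non-compliance and viral failure it removes women who could still be followed, against the intent of 8.3 and 11.6. Applied before week 48, it can cost the primary-endpoint scan for plausibly informative reasons.

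The size cannot be derived from the documents. Under the assumed shares the retained-only estimate would be 0.01 to 0.10 points above the as-randomised difference, or 1 to 10% of the 1-point target, and equal to it if the effect is fully kept.

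Three stronger readings are not supported:

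- That all three triggers contradict 8.3. Only refusal does; the other two are qualified, and 11.7 narrows the viral-failure route.
- That the rule biases one arm against the other. The trial is open-label, so this is possible, but the documents give nothing on how exits would split by arm.
- That retaining these women restores power from 75.8% to 80.1%. That requires them to keep the whole effect; if they keep none, power at f = 10% is 71.4%.

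**What to change.** In section 10, list reasons for stopping study drug separately from reasons for ending follow-up. Limit the second list to withdrawal of consent to follow-up, loss to follow-up, death, sponsor termination, or a clinician's judgement that follow-up itself is harmful. State that consenting women in both arms who stop drug or change regimen keep the scheduled week-48 and week-96 DXA and are analysed as randomised, with no DXA during pregnancy (11.9 already requires pregnant women to stop TAF/FTC). In 11.6, have the woman withdrawn from study drug rather than from the study.

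The cost is wording in two sections plus DXAs already on the schedule. The real downside is dilution: with an assumed 10% stopping and keeping none of the effect, power is 71.4%, against 75.8% if they are simply missing and the rest show the full effect; if they keep half, it is 76.0%. The sponsor would be choosing a clear as-randomised comparison with less risk of bias, not more power. Label: cheap improvement.

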11. ASSESSMENT OF SAFETY

11.1 Adverse Events (AEs)

Adverse events (AEs) are defined as any untoward medical occurrence in a participant that does not necessarily have a causal relationship with the study medication/intervention. An AE can therefore be any unfavourable and unintended sign (including abnormal laboratory finding), symptom, or disease temporally associated with the use of study drug/intervention, whether or not it is related to the medication/intervention.

Toxicities will be graded on a 4-point scale according to standard guidelines outlined in the “Division of AIDS Table for Grading the Severity of Adult and Pediatric Adverse Events”⁴⁸[Appendix C]. In general, grade 1 and 2 events will not be considered adverse events, but details should be documented in the source documents. Fractures will be considered and captured as an adverse event regardless of grading.

Stable chronic conditions which are present prior to clinical study entry and do not worsen are not considered adverse events and will be accounted for in the participant's medical history.

Participants who have an adverse event should be followed and treated by the site Investigator until the abnormal parameter or symptom has resolved or stabilized. It is up to the clinician to determine that the AE is either resolved or that it has reached a stable state, after which no further follow-up is necessary. There should also be source documentation to support this determination.

Rates of adverse events, serious adverse events and hospitalisations will be compared between the two arms. Specific attention will be paid to HIV RNA (see below), CD4 cell counts, and metabolic parameters such as fasting glucose, and lipid profiles.

The most common adverse reactions of moderate to severe intensity and incidence $\geq 2\%$ in those receiving TAF are headache, fatigue, nasal congestion and diarrhea.

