1.4 Potential risks and benefits to participants

Tenofovir alafenamide as an individual agent has been administered to more than 40 HIV-positive participants in two separate studies. In study GS-US-120-1101, participants received higher doses of TAF (50 mg and 150 mg) than the TAF dose in this study. Side effects that were seen in more than two participants were headache, nausea, and gas (flatulence). In study GS-US-120-0104, adverse events observed in more than two participants were nausea and fatigue. One serious adverse event of chest pain was reported, but not considered related to study drugs.²⁸

In addition, F/TAF has been given to over 3000 HIV infected participants in switching studies²¹⁻³. In these trials, there was no new toxicity observed relative to TDF/FTC and less than 1 % had to discontinue medication secondary to adverse events. The most frequently described adverse events occurring in more than 5% of persons included headache, diarrhea, nasal congestion, and fatigue.

A study in dogs detected eye problems (posterior uveitis- inflammation in the back of the eye) in some dogs when TAF was given at the highest doses. There have not been cases of uveitis related to TAF in clinical studies.²⁸

TAF is a drug similar to Tenofovir disoproxil fumarate (TDF), Viread®, an approved medication by the FDA for the treatment of HIV and hepatitis B infection²⁹. The side effects for TAF are expected to be similar to Viread®. The side effects for Viread® are listed below.

Tenofovir DF (TDF, Viread®)

Tenofovir DF has been studied in more than 12,000 HIV-infected adults for as long as 480 weeks in some patients. Common potential side effects identified in patients who received at least one dose of tenofovir DF 300 mg include diarrhea, nausea, vomiting, flatulence (intestinal gas), and dizziness. Those side effects were often mild or moderate in severity, and did not lead to discontinuation of tenofovir DF.²⁹

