11.2 Recording/ Documentation of AEs

At each contact with the participant, information regarding adverse events will be elicited by appropriate questioning and examinations, and will be recorded immediately on a source

Protocol IN-CA-311-3963/CTN 299: Version 5.0 Date: March 19, 2019

Page 30 of 53

document (e.g., progress notes, laboratory reports, survey tools, and data collection tools). The start date, stop date, severity of each reportable event, and the PI's judgment of the AE's relationship to the study medication/intervention will also be recorded in the case report form (CRF).

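### Section 11.1 does not count grade 1 and 2 events as adverse events, so moderate cases of the TAF reactions it lists would be left out of its comparison of rates between arms

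*Combined protocol and SAP*

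**What the plan says.** Four statements in section 11.1 bear on this point.

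- **Definition.** "Adverse events (AEs) are defined as any untoward medical occurrence in a participant that does not necessarily have a causal relationship with the study medication/intervention". No severity limit is attached.
- **Grade rule.** "Toxicities will be graded on a 4-point scale according to standard guidelines", and then "In general, grade 1 and 2 events will not be considered adverse events, but details should be documented in the source documents". Fractures are the one stated exception and count at any grade.
- **Planned use.** "Rates of adverse events, serious adverse events and hospitalisations will be compared between the two arms".
- **Expected reactions.** "The most common adverse reactions of moderate to severe intensity and incidence" of at least 2% "in those receiving TAF are headache, fatigue, nasal congestion and diarrhea".

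Section 11.2 sends to the case report form the dates, the causality judgement and the "severity of each reportable event". It does not say which events are reportable. Section 5.5 lists safety, meaning clinical and laboratory adverse events, as a secondary endpoint. Section 1.4 expects TAF's side effects to resemble those of TDF, and says of the common TDF effects: "Those side effects were often mild or moderate in severity, and did not lead to discontinuation of tenofovir DF".

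**The concern.** The definition and the grade rule cannot both decide what counts. If the grade rule governs, the adverse-event rate in each arm excludes mild and moderate events. The section's own list of expected TAF symptoms begins at moderate. Moderate headache, fatigue, nasal congestion or diarrhea would be written in the source notes, would not be an adverse event, and so would not enter the rate that is compared.

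The qualifier that the rule applies in general adds a second difficulty. No criterion says when a grade 1 or 2 event does count. The trial is open-label (section 5.0), so site staff would make that choice knowing the arm.

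The risk is one of description. Low counts produced partly by the counting rule could be read as evidence that the two regimens are equally well tolerated.

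**Working it through.** **Inputs**

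- Women per arm: 64 (section 13.1).
- Incidence of each listed reaction at moderate or severe intensity: at least 2% (section 11.1), used here as 2%.
- Moderate equals grade 2, and severe means grade 3 or 4: an assumption. Section 11.1 mentions a 4-point scale but prints no mapping of words to grades.
- Share of the moderate-or-severe cases that are severe: not in the documents. It is varied from 5% to 50%.
- All 64 women are treated as followed.

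**The plan's own figure.** For a difference of 1%, SD 2%, 80% power and a two-sided 5% level (the plan does not state sidedness), the two-sample t test needs 63.77 women per arm. That rounds up to 64 per arm and 128 in total, so the stated sample size reproduces. The plan gives no figure for the adverse-event comparison.

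**Cases expected for each listed reaction, per arm**

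Expected count = 64 × 0.02 × share counted.
Chance of no counted case in an arm = (1 − 0.02 × share counted)^64.

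| What is counted | Expected cases per arm | Chance of none in the arm |
|---|---|---|
| Grade 2 and higher (all) | 64 × 0.02 = 1.28 | 27% |
| Grade 3–4, 50% severe | 0.64 | 53% |
| Grade 3–4, 25% severe | 0.32 | 73% |
| Grade 3–4, 10% severe | 0.13 | 88% |
| Grade 3–4, 5% severe | 0.06 | 94% |

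The share of cases left out is 1 minus the severe share, so 50% to 95% over the assumed range.

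**Would counting grade 2 let the trial detect a difference?** Take the four reactions together at 4 × 2% = 8% (no overlap) in one arm and half that, 4%, in the other. With 64 per arm and a two-sided 5% level, the normal approximation runs as follows.

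- Standard error under no difference: √(2 × 0.06 × 0.94 / 64) = 0.0420.
- Standard error under the alternative: √((0.08 × 0.92 + 0.04 × 0.96) / 64) = 0.0418.
- Power = Φ((0.04 − 1.96 × 0.0420) / 0.0418) = Φ(−1.01), about 16%.

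With grade 3–4 only, the same calculation gives about 4% to 10% over the assumed severe shares, and the approximation is poor at such small counts. Power is low under either rule.

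**Do other routes recover these symptoms?** Section 5.5 collects BMD, renal measures, lipids and viral load separately. Fractures count at any grade, and serious events and hospitalisations are counted in their own right (11.1, 11.3). None of these records a moderate headache or a moderate episode of diarrhea. The named tolerability measure is the EuroQoL, given at weeks 0, 48 and 96 (section 8.7). It is a general quality-of-life questionnaire and does not give event rates.

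**The case against.** A reader might infer that the comparison would miss most of the known harms of TAF, or that it would show rates near zero and so a false equality. The documents do not support either reading, and several objections to them stand.

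- **The main harms are covered elsewhere.** Bone, renal, lipid and virologic effects, serious events and hospitalisations are all captured without the grade threshold. The point reaches only the listed symptoms.
- **The size of the loss is not known.** No moderate/severe split is given, so the 50% to 95% range is an illustration. Section 1.4 supports the direction, since TDF effects were often mild or moderate and TAF's are expected to be similar, but it gives no percentages.
- **The incidence above 5% in section 1.4 cannot be used for this.** It would give 64 × 0.05 = 3.2 women per arm, but it carries no severity limit. Part of it may be grade 1, which counting grade 2 would not recover.
- **No difference between arms is shown to be at risk.** Section 1.4 reports no new toxicity against TDF/FTC in the switching studies. Section 13.3 summarises other secondary endpoints without formal comparison.
- **A higher threshold has a purpose.** In an open-label trial, subjective moderate symptoms are open to reporting bias, and a threshold applied equally to both arms limits it.
- **The information is kept.** Lower-grade details go into source documents, and changes in clinical condition are captured at visits (sections 8.3 and 8.7).

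The last objection answers only half the point. An event that is noted but is not an adverse event under 11.1 still does not enter the adverse-event rate. The bias objection is a reason to show two thresholds. It does not explain why the section's definition, grade rule and planned comparison disagree.

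**Conclusion.** The point holds in a limited form. Section 11.1 contradicts itself on what an adverse event is. If the grade rule is followed, and moderate is read as grade 2, moderate cases of the four listed reactions drop out of a comparison that the same section plans and that serves a secondary endpoint. At 2% incidence, the expected count per reaction per arm falls from about 1.3 to about 0.06–0.64, for an assumed severe share of 5% to 50%.

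The primary BMD endpoint is not affected. Because power is low under either rule, the gain from a change is an honest account of symptomatic tolerability, not a better chance of detecting a difference. The change is worth making because it is cheap and prevents low counts from being read as equal tolerability.

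**What to change.** 1. In 11.1, reconcile the definition of an adverse event with the grade rule. In 11.2, define which events are reportable.
2. For recording and tabulation only, with no change to clinical management, enter clinical events of grade 2 and higher on the case report form from the source notes that sites must already keep. At minimum, do this for headache, fatigue, nasal congestion and diarrhea.
3. Report rates by arm at grade 2 or higher, and separately at grade 3 or higher.
4. If this is not adopted, state in 11.1 that the comparison covers only grade 3–4 events plus fractures, and that it does not support a conclusion of equal tolerability.

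The cost is a wording change and some extra data entry; no visit, test or staff is added. The downside is more event records per woman, and grade 2 symptoms that women may report differently because they know their arm. Showing both thresholds lets the reader judge that.
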